5.2 EFFECTIVENESS

5.2.1 Endpoint(s) of effectiveness

The main effectiveness endpoint in this study is the change from baseline in HbA_{1c} after 24 weeks of treatment.

The other effectiveness endpoints are the following:

- Occurrence of treat to target effectiveness response, that is an HbA_{1c} under treatment of < 6.5% after 24 weeks of treatment.
- Occurrence of relative effectiveness response (HbA_{1c} lowering by at least 0.5% after 24 weeks)
- Change from baseline in fasting plasma glucose (FPG) after 24 weeks of treatment

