5.1 Effectiveness Assessment Criteria

- The change from baseline to last visit[†] of HbA1c
- Achievement rate of target effectiveness (HbA1c of < 6.5% at last visit)
- Achievement rate for target of reduction (At least 0.5% HbA1c lowering at last visit)
- The change from baseline to last visit of FPG
- Final effectiveness assessment

Defines the final effectiveness assessment (Improved, No changed, Worsened, Uevaluable) based on both HbA1c and FPG that measured at baseline and last visit. The final effectiveness assessment is as the following criteria:

- Improved: In case the symptoms, such as symptoms of improvement or maintenance[†], are judged
 - I. In the last visit compared to the baseline, in case the both HbA1c and FPG are maintained or decreased
 - II. In the last visit compared to the baseline, in case the HbA1c is maintained or decreased and the FPG is increased
 - III. In the last visit compared to the baseline, in case the HbA1c is increased and the FPG is maintained or decreased
- No changed: In case there is no significant change between baseline and last visit, that is, in case it is not judged to be maintenance effect
 - I. In the last visit compared to the baseline, in case the HbA1c is increased, but the FPG is unknown
- Worsened: In case the symptoms are worse in the last visit compared to the baseline
 - I. In the last visit compared to the baseline, in case the both HbA1c and FPG are increased
- Not evaluable: In case the collected information is insufficient and the final effectiveness

	CONFIDENTIAL :	Last Update Date
	THIS DOCUMENT AND INFORMATION CONTAINED HEREIN IS PROPRIETARY TO COMPANY AND IS NOT TO BE DISCLOSED WITHOUT THE WRITTEN PERMISSION OF COMPANY.	21-AUG-2017
STATISTICAL ANALYSIS PLAN(V3.0)		

assessment can not be classified as 'Improved', 'No changed' or 'Worsened'

† Maintenance: In case the symptoms are likely to worsen when the administration of Trajenta is interrupt, or, in case the same effect is continue when replacing to existing drugs, etc.

‡ Last visit: The last visit point that measured HbA1c after administration of Trajenta

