6.2 Effectiveness Analyses

Effectiveness analysis shall be conducted for subjects of the effectiveness analysis set.

The change from baseline to last visit of HbA1c will be calculated for each subject. The difference of HbA1c between baseline and last visit shall be described by mean, and shall be analyzed with paired t-test.

According to the following baseline characteristics, the change from baseline to last visit of HbA1c will be analyzed with t-test or ANOVA (Analysis of Variance).

- Age, Gender, Pregnancy, Allergy, Diabetes mellitus complications and their classification, Other medical history and its classification, duration of T2DM, Family history, Pediatric group (Under 19 years), Geriatric group (65 years or older), Kidney disorder, Liver disorder, Subjects whose drug administration period of long-term (24 weeks or more), Concomitant medication and its classification, Total administration period of Trajenta, Reason of prematurely study withdrawal, Other anti-diabetic agent and its classification

If necessary, analysis for the impact of the change from baseline to last visit of HbA1c may be carried out using multiple regression analysis. In general, the variables corresponding to the baseline characteristics listed in section 6.1 are used as an independent variable. However, as considering the structure and characteristics of the collected data, the variables used for the actual analysis can be added or subtracted.

The frequency and percentage of the final effectiveness assessment will be summarized.

The final effectiveness assessment of “Improved” will be classified as “Effective”. The final effectiveness assessment of “No changed” and “Worsened” will be classified as “Ineffective”. The effectiveness rate and its 95% confidence intervals will be estimated with exact method.

The effectiveness rate will be analyzed according to the baseline characteristics listed in section 6.1. Chi-square test or Fisher’s exact test will be used for comparing between subcategories of each baseline characteristic and will be estimated with its 95% confidence interval.

According to the following subgroup, the frequency and percentage of subjects whose HbA1c of <

	CONFIDENTIAL :	Last Update Date
	THIS DOCUMENT AND INFORMATION CONTAINED HEREIN IS PROPRIETARY TO COMPANY AND IS NOT TO BE DISCLOSED WITHOUT THE WRITTEN PERMISSION OF COMPANY.	21-AUG-2017
STATISTICAL ANALYSIS PLAN(V3.0)		

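### The final effectiveness assessment goes by the direction of change alone, so its 'Effective' rate would be well above half with no drug effect and needs a companion rate based on a real HbA1c fall

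*SAP*

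**What the plan says.** SAP 4.1 lists the final effectiveness assessment as an effectiveness endpoint, and SAP 5.1 defines it from HbA1c and FPG at baseline and last visit.

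- **Improved** has three rules: "in case the both HbA1c and FPG are maintained or decreased"; "in case the HbA1c is maintained or decreased and the FPG is increased"; and "in case the HbA1c is increased and the FPG is maintained or decreased".
- **No changed** is introduced as "No changed: In case there is no significant change between baseline and last visit", but its single rule is "in case the HbA1c is increased, but the FPG is unknown".
- **Worsened** has one rule: "in case the both HbA1c and FPG are increased".
- **Not evaluable** takes what the collected information cannot classify.

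No rule states how large a change must be. The footnote on maintenance speaks of what symptoms would do if the drug were interrupted or replaced; it gives no numeric band.

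SAP 6.2 maps Improved to Effective, and No changed and Worsened to Ineffective. It adds that "The effectiveness rate and its 95% confidence intervals will be estimated with exact method", and compares the rate across the baseline characteristics of SAP 6.1 by chi-square or Fisher's exact test. Elsewhere the documents do use a size of response: Protocol 5.2.1 has "HbA_{1c} lowering by at least 0.5% after 24 weeks", and SAP 5.1 applies the same 0.5 threshold at last visit. In SAP 6.2 and 7.3 that rate, and the rate of HbA1c below 6.5%, are given as frequency and percentage only.

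**The concern.** A rule based on sign alone lets random variation decide the label of a patient who has not really changed. The category whose heading describes such a patient is closed to anyone with both markers measured, so he or she is labelled Improved or Worsened. Since three of the four sign combinations count as Effective, the rate starts from a high base even if nothing happens on average.

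This is the only effectiveness proportion with a confidence interval. Protocol 3.2 describes a single-arm study, and no reference rate is stated. A high rate with a narrow interval could therefore be taken as evidence of effect when the rule itself supplies much of it.

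**Working it through.** **No figure to reproduce.** Neither document states an expected effectiveness rate, SD, correlation or power.

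**Inputs from the SAP.** Effective means Improved. With both markers known, a patient is not Improved only if both rise, so Effective = 1 − P(HbA1c rises and FPG rises). I read 'maintained' as equal at the reported precision.

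**Assumptions not in the documents.** Zero mean change in both markers; bivariate normal changes; both markers measured; HbA1c change SD 0.5 to 1.0 points, rounded to 0.1; FPG change SD 25 to 40 mg/dL, rounded to 1; correlation ρ from 0 to 0.8.

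**Step 1, ignoring ties.** P(both rise) = 1/4 + arcsin(ρ)/(2π). Effective is then 75.0% at ρ = 0, 70.2% at 0.3, 66.7% at 0.5, 64.8% at 0.6 and 60.2% at 0.8.

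**Step 2, with ties from rounding.** At ρ = 0, HbA1c SD 0.8 and FPG SD 30, P(HbA1c rises) = 1 − Φ(0.05/0.8) = 0.475 and P(FPG rises) = 1 − Φ(0.5/30) = 0.493. Effective = 1 − 0.475 × 0.493 = 76.6%. Simulation with 2 million draws per scenario gives:

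| HbA1c change SD | ρ = 0 | 0.3 | 0.5 | 0.6 | 0.8 |
|---|---|---|---|---|---|
| 0.5 | 77% | 72–73% | 69% | 67% | 63% |
| 0.8 | 76–77% | 72% | 68% | 66% | 62% |
| 1.0 | 76% | 71–72% | 68% | 66% | 62% |

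The range is about 62–77%.

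**Step 3, which rule supplies it.** The share with HbA1c not risen is Φ(0.05/SD): 54.0%, 52.5% and 52.0% for SD 0.5, 0.8 and 1.0. The remainder comes from the discordant rule (HbA1c up, FPG not up). At SD 0.8 that is 76.6 − 52.5 = 24 points at ρ = 0 and about 62 − 52.5 = 9 to 10 points at ρ = 0.8.

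**Step 4, the documents' own threshold.** With no effect, a rounded fall of at least 0.5 has probability Φ(−0.45/SD): 18%, 29% and 33% for the three SDs. This is not zero either, but it is far lower.

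**Step 5, what moves the figure.**

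- *Missing FPG lowers it.* HbA1c increased with FPG unknown counts as Ineffective. HbA1c not increased with FPG unknown is not listed under any rule. If a fraction m lacks FPG and the unlisted half leaves the denominator, then (ignoring ties) the rate is (1 − m)(1 − P(both rise))/(1 − m/2). With m = 0.2 and ρ = 0 this is 0.8 × 0.75/0.9 = 66.7%; at ρ = 0.7 it is 55.7%.
- *Regression to the mean raises it.* A mean fall of 0.2 SD in both markers gives 70–82% (ρ 0.7 to 0).
- *Average worsening lowers it only in part.* A mean rise of 0.2 SD in both markers still gives 54–66% (ρ 0.7 to 0).

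**Step 6, apparent precision.** If all 3,000 planned patients were evaluable and 70% were Effective, the half-width by the normal approximation is 1.96 × √(0.7 × 0.3/3000) = 1.6 points. The interval of about 68–72% lies wholly within the no-effect range.

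**The case against.** Protocol 7.1 and 7.2 make every analysis descriptive, with no hypotheses. The main endpoint is HbA1c change, and the below-6.5%, at-least-0.5 and FPG results are reported without this rule. SAP 5.1 counts maintenance as a good outcome on purpose, including when the drug replaces an existing one, and SAP 6.2 analyses patients with prior DPP-4 inhibitor use separately. A stable patient after a switch is a reasonable thing to call a success. The percentages rest on assumed SDs, correlation and complete FPG, although Protocol 7.4 says no investigations are required.

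Most of this stands. It limits the severity and rules out redefining Improved as a fall of at least 0.5, which would override the maintenance definition, drop FPG and repeat an existing endpoint. It does not answer two things. The No changed heading and rule contradict each other. And the one effectiveness proportion given an interval has a high, unstated value under no effect.

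A reader might infer that the absence of a margin produces the whole 62–77%. It does not: 9 to 24 points come from the discordant rule, and the other 52–54% is mostly the symmetry of a sign rule. A tolerance on 'maintained' makes matters worse. Allowing HbA1c rises up to 0.3 gives 71–84% with no effect (ρ 0.7 to 0). Counting any change under 0.5 either way as maintained gives 67–82% on HbA1c alone.

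**Conclusion.** The concern holds as a defect of definition and presentation in one descriptive endpoint. Three parts need no assumption: the rules use direction only, three of four sign combinations are Improved, and No changed cannot occur when both markers are known. The size, about 62–77% Effective with no drug effect, is conditional on zero mean change, both markers measured, HbA1c change SD 0.5 to 1.0 and correlation 0 to 0.8. Missing FPG would lower it and regression to the mean would raise it.

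It would go too far to say that an ineffective drug would score a particular percentage in this study, since the documents give none of the inputs. Nor do they support saying that the effectiveness results as a whole are compromised, or that counting stable patients is itself an error. It is a stated choice, but the reported rate should make it visible.

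**What to change.** Keep the category that counts maintenance and make these changes in the SAP.

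1. **6.2 and 7.3:** split Improved into (a) HbA1c fallen by at least 0.5, (b) HbA1c unchanged or fallen by less than 0.5, and (c) HbA1c risen with FPG not risen. Give the effectiveness rate and exact 95% interval for all Improved and for (a) alone. Do not widen 'maintained' to take in HbA1c rises.
2. **5.1:** reconcile the No changed heading with its rule, either by moving HbA1c increased with FPG unknown to Not evaluable or by renaming the category. Say where HbA1c not increased with FPG unknown belongs, and whether Not evaluable patients are in the denominator. The choice matters: if the Not evaluable are left out, moving the first group there raises the 20%-missing example at ρ = 0 from 66.7% to 0.8 × 0.75/0.8 = 75%.
3. **6.2:** state that the Improved rate includes maintenance and cannot be read as drug effect without a comparator. Do not print a fixed no-effect rate unless its assumptions are given.

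The cost is SAP wording, a few table rows from data already collected, and a lower companion rate beside the headline. With both markers known, (a) has the same numerator as the existing at-least-0.5 endpoint; the gain is an interval and its place next to the Improved rate.

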3.2 Effectiveness Analysis Set

The subjects below shall be excluded from effectiveness analysis set in the following order:

- (1) Subjects who excluded from safety analysis set
- (2) Missing HbA1c value at both baseline and after administration of Trajent

4. Endpoints

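### The SAP's effectiveness rate counts a patient whose HbA1c rose as a success if FPG did not rise and as a failure if FPG is unknown, and no listed rule covers a non-rising HbA1c with unknown FPG

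*SAP*

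**What the plan says.** SAP 5.1 builds a four-category final effectiveness assessment from the direction of change in HbA1c and FPG between baseline and last visit.

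- **Improved** has three rules. Rule I: "in case the both HbA1c and FPG are maintained or decreased". Rule II: "in case the HbA1c is maintained or decreased and the FPG is increased". Rule III: "In the last visit compared to the baseline, in case the HbA1c is increased and the FPG is maintained or decreased".
- **No changed** has one rule: "in case the HbA1c is increased, but the FPG is unknown".
- **Worsened** has one rule: both markers increased.
- **Not evaluable** is the remainder, for insufficient information that fits none of the other three categories.

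SAP 6.2 maps 'Improved' to 'Effective', and 'No changed' and 'Worsened' to 'Ineffective'. 'Not evaluable' is mapped to neither. On the analysis: "The effectiveness rate and its 95% confidence intervals will be estimated with exact method". The rate is also compared across the baseline characteristics by chi-square or Fisher's exact test.

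A patient can enter this analysis without FPG. Beyond safety-set exclusions, SAP 3.2 excludes only on HbA1c ("Missing HbA1c value at both baseline and after administration of Trajent"), and the last visit is defined by HbA1c alone ("The last visit point that measured HbA1c after administration of Trajenta"). Protocol 5.2.2 asks for FPG at baseline, 12 and 24 weeks, but Protocol 7.4 says that no investigation is required, and SAP 6.4 rules out imputation. Protocol 5.2.1 names HbA1c change as the main effectiveness endpoint and does not list the final effectiveness assessment.

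**The concern.** Three features of the rules matter.

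1. With both markers known, only a rise in both is a failure. A patient who got worse on the main effectiveness marker is reported as effectively treated if FPG held steady or fell.
2. The same HbA1c rise becomes a failure when FPG was not measured. A missing laboratory value, not the patient's course, decides the class.
3. The mirror case, HbA1c maintained or decreased with FPG unknown, has no rule. Two programmers could derive different rates from the same data.

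The result is labelled an effectiveness rate, carries an exact interval, and is tested across many subgroups. Subgroups that differ in how often FPG is tested could show different rates with the same true effect.

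**Working it through.** The documents state no effectiveness rate, so there is no figure to reproduce.

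**Step 1: enumerate the cells from SAP 5.1 and 6.2.**

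| HbA1c | FPG | Category | Counted as |
|---|---|---|---|
| not risen | not risen | Improved (I) | Effective |
| not risen | risen | Improved (II) | Effective |
| risen | not risen | Improved (III) | Effective |
| risen | risen | Worsened | Ineffective |
| risen | unknown | No changed | Ineffective |
| not risen | unknown | no listed rule | unstated |

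Every 'Improved' rule names an FPG direction, and the 'No changed' and 'Worsened' rules need an HbA1c rise. Read literally, the last row falls by elimination to 'Not evaluable'. Yet rules I and II together give 'Improved' whichever way FPG moved.

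**Step 2: assumed inputs, none from the documents.** Changes are bivariate normal with SD 1.0 (HbA1c, percentage points) and 40 mg/dL (FPG) and correlation rho. They are rounded to 0.1 and 1 mg/dL, with ties counted as maintained. FPG is missing independently of outcome in a share m of patients.

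Let H = P(HbA1c rises) and P = P(both rise). Rule III patients are H − P.

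- Effective = (1−m)(1−P)
- Ineffective = (1−m)P + mH
- Uncovered cell = m(1−H)

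**Step 3: no true change, complete FPG.** H = 48%, so HbA1c alone gives 52%. The SAP rate 1 − P is 76/71/68/64/58% at rho 0/0.3/0.5/0.7/0.9, so rule III adds 24/19/16/12/6 points. As a check, without rounding 1 − [1/4 + arcsin(rho)/(2π)] gives 75/70/67/63/57%, against 50%. If mean HbA1c instead rises by 0.3 with FPG unchanged, the rate is still 66/62/58% at rho 0.3/0.5/0.7, against 40% on HbA1c alone.

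**Step 4: HbA1c fall 0.5, FPG fall 15 mg/dL, rho 0.5.** P = 17.1%, H = 29.1%, rule III = 12.0%. At m = 20%:

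- Effective = 0.8 × 0.829 = 66.3%
- Ineffective = 0.8 × 0.171 + 0.2 × 0.291 = 19.5%
- Uncovered cell = 0.2 × 0.709 = 14.2%
- Uncovered cell dropped: 66.3/(66.3 + 19.5) = 77%
- Uncovered cell 'Improved': 66.3 + 14.2 = 80.5%

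| Handling | m = 0% | 20% | 40% |
|---|---|---|---|
| Uncovered cell dropped | 83% | 77% | 69% |
| Uncovered cell 'Improved' | 83% | 80.5% | 78% |
| Uncovered cell 'Improved', rule III not Effective (1 − H) | 71% | 71% | 71% |
| Both FPG-unknown cells dropped (1 − P) | 83% | 83% | 83% |

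**Step 5: subgroup comparison.** Take two subgroups of 1,000 (assumed) with the Step 4 effect, tested at two-sided 0.05, with the uncovered cell dropped. At 10% v 20% missing the rates are 80.3% and 77.3%. Evaluable patients are 1,000 × (1 − 0.1 × 0.709) = 929 and 1,000 × (1 − 0.2 × 0.709) = 858. The pooled rate is 78.9%, and the standard error is √[0.789 × 0.211 × (1/929 + 1/858)] = 1.93 points. The difference of 3.03 points gives z = 1.57 and significance in about 35% of repeats. Other contrasts give about 7% (2% v 5%), 12% (10% v 15%) and 90% (10% v 30%). If the uncovered cell is 'Improved', 10% v 30% gives about 27%.

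**The case against.** **Rule III is a deliberate choice.** The assessment is defined on both markers, and 'Improved' covers maintenance as well as improvement, with a footnote on replacing existing drugs. How to class discordant markers is partly a matter of preference. Some of the HbA1c rises will also be small: in the Step 4 example about 40% of rule III patients rise by 0.3 or less. The April 2017 SAP revision that added the assessment also cites regulatory guidance, but the documents do not show whether that guidance prescribes these categories. This stands. A reader might infer that rule III is simply a mistake to be struck out. The documents do not support that. They support showing how much of the rate rests on it.

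**The uncovered cell may already be meant as 'Improved'.** The residual category begins "Not evaluable: In case the collected information is insufficient and the final effectiveness" and applies only where no other class fits. Since rules I and II agree whatever FPG did, the information can be called sufficient. This also stands. It would go too far to say that the SAP sends these patients to 'Not evaluable': that is the literal reading by elimination, and the larger losses (77% and 69%) depend on it. The dependence on FPG testing remains on either reading, but it is smaller on this one.

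**The denominator.** Keeping 'Not evaluable' patients in the denominator would give still lower rates (66% at 20% missing). The mapping in SAP 6.2 suggests that they are left out, so no weight is placed on that figure.

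**Size and consequence.** SDs, correlation, missingness and subgroup sizes are all assumed. FPG is scheduled alongside HbA1c at every visit, so missingness may be low, and at 2% v 5% the subgroup distortion is slight. Protocol 7.1 makes all analyses descriptive. These points limit the weight of the concern but do not remove it.

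**Conclusion.** The point holds and should be fixed. Confidence is high that rule III counts HbA1c rises as successes while the same rise with FPG unknown is a failure, since both are explicit. Confidence is moderate on the uncovered cell, which is ambiguous.

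On the assumed inputs, rule III adds 6 to 24 points when nothing has truly changed, and 12 points in the example with a true benefit. Missing FPG pulls the other way: at 20% missing it lowers the example rate by about 2 to 6 points, depending on the reading. The two effects have different drivers, correlation and missingness, and cannot be relied on to cancel. Subgroup distortion is small unless FPG missingness differs by about 10 points or more, and the documents do not say whether it does.

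A reader might infer that the study's effectiveness results as a whole are compromised. They are not: the consequence stops at this one rate, its interval and its subgroup tests.

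**What to change.** 1. Assign HbA1c maintained or decreased with FPG unknown explicitly to 'Improved', as rules I and II imply.
2. Report the rate, its interval and its subgroup comparisons twice, with and without rule III patients counted as 'Effective', and give their number. In the second version they stay in the denominator as not effective. Combined with item 1, that version follows HbA1c direction and does not move with random FPG missingness.
3. As a clarification, state that 'Not evaluable' is outside the denominator, and show its count overall and by subgroup.

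An alternative that keeps rule III is to send both FPG-unknown cells to 'Not evaluable' and drop them. This also removes the dependence on random missingness, but it discards patients with known HbA1c and leaves HbA1c rises among the successes.

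The cost is SAP wording, a few lines of derivation code, a slightly longer table and a less favourable second figure (83% to 71% in the example). The second version sets FPG aside in the Effective/Ineffective split, which is why both should be shown. Even then the rate is about 52% with no true change, so it should be labelled as a descriptive measure added by the SAP.

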Proprietary confidential information. © 2017 Boehringer Ingelheim International GmbH or one or more of its affiliated companies.

Name of company/Marketing Authorisation Holder: Boehringer Ingelheim Korea		Tabulated Study Protocol	
Name of finished product: Trajenta			
Name of active ingredient: Linagliptin			
Protocol date: 1 December 2011	Trial number: 1218.104/UXX-XXXX		Revision date: 22 Feb 2017
Duration of treatment:	1) Treatment duration for short-term surveillance: 12±2 weeks, long-term surveillance: 24±2 weeks. 2) Study duration: 6 years. (KFDA set Trajenta re-examination period from 14 Sep 2011 to 13 Sep 2017. Interim report planned biannually for the initial two years and annually thereafter by Dec 2017.)		
Criteria for effectiveness:	1. Main endpoint 1) Change from baseline in HbA1c after 24 weeks of treatment. 2. Other endpoint 1) Occurrence of treat to target effectiveness response, that is an HbA1c under treatment of < 6.5% after 24 weeks of treatment. 2) Occurrence of relative effectiveness response (HbA _{1c} lowering by at least 0.5% after 24 weeks) 3) Change from baseline in fasting plasma glucose (FPG) after 24 weeks of treatment		
Criteria for safety:	All reported adverse events including hypoglycemic events in patients who take at least one dose of Trajenta will be noted. Endpoints pertaining to safety will be presented as incidence rates of adverse events		
Statistical methods:	Descriptive statistics		

FLOW CHART

Data points	Baseline	Follow-up 1	Follow-up 2
Visit Number	1	2	3
Week/s	0	12±2	24±2
Diagnosis	X		
Inclusion / exclusion criteria	X		
Demographics	X		
Diabetes mellitus complications	X		
Other medical history	X		
Anti-hyperglycemic agents	X	X	X
Concomitant medications	X	X	X
Trajenta administration status	X	X	X
Renal function	X [^]		
Effectiveness endpoints	X	X	X
Changes in lab tests		X [^]	X [^]
Adverse events		X	X
Study completion		X	X

[^]: If applicable.

TABLE OF CONTENTS

TITLE PAGE	오류! 책갈피가 정의되어 있지 않습니다.
NON-INTERVENTIONAL STUDY PROTOCOL SYNOPSIS	2
FLOW CHART	4
TABLE OF CONTENTS	5
ABBREVIATIONS	8
1. INTRODUCTION	9
1.1 MEDICAL BACKGROUND	9
1.2 DRUG PROFILE	9
2. RATIONALE, OBJECTIVES, AND BENEFIT-RISK ASSESSMENT	10
2.1 RATIONALE FOR PERFORMING THE STUDY	10
2.2 STUDY OBJECTIVES	10
2.2.1 Primary objective	10
2.2.2 Secondary objective	10
2.3 BENEFIT-RISK ASSESSMENT	10
3. DESCRIPTION OF DESIGN AND STUDY POPULATION	11
3.1 OVERALL DESIGN AND PLAN	11
3.1.1 Administrative structure of the study	11

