5.2.2 Assessment of effectiveness

HbA_{1c}:

HbA_{1c} should be collected within 1 month prior to baseline and after 12 weeks and 24 weeks of treatment.

Fasting plasma glucose (FPG):

FPG should be collected within 1 month prior to baseline and after 12 weeks and 24 weeks of treatment.

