6. SURVEILLANCE PLAN

6.1 VISIT SCHEDULE

The flow chart at the front of the protocol summarizes the data to be collected at each visit (recommended visit schedule - Visit 2 : 12±2 weeks/ Visit 3 : 24±2 weeks). The procedures are further described below.

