7.3.2 Main analyses of effectiveness

A descriptive analysis of endpoints is planned. For patients treated with Trajenta, the change of HbA_{1c} from baseline and last follow-up visit will be calculated. Effectiveness analyses will be performed based on demographics and baseline characteristics.

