7.3.3 Other analyses of effectiveness

A descriptive analysis of effectiveness endpoints is planned. For patients treated with Trajenta, the occurrence of treat to target effectiveness response, that is an HbA_{1c} under treatment of < 6.5% and relative effectiveness response (HbA_{1c} lowering by at least 0.5%)

Proprietary confidential information. © 2017 Boehringer Ingelheim International GmbH or one or more of its affiliated companies.

after 24 weeks will be calculated. In addition, the change of FPG from baseline and last follow-up visit will be calculated. Effectiveness analyses will be performed based on demographics and baseline characteristics.

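### The SAP computes the two HbA1c responder rates at the last visit with any HbA1c, where the protocol says after 24 weeks; the protocol leaves the timing of HbA1c and FPG change ambiguous, and no table gives the Visit 3 result

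*SAP*

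**What the plan says.** **Endpoint definitions.** The protocol synopsis gives "Main endpoint 1) Change from baseline in HbA1c after 24 weeks of treatment". Protocol 5.2.1 times all four endpoints the same way: HbA1c change, HbA1c "under treatment of < 6.5% after 24 weeks of treatment", HbA1c lowering of at least 0.5%, and FPG change.

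**Protocol analysis sections.** For the two responder rates, 7.3.3 keeps the timing: "after 24 weeks will be calculated". For HbA1c change, 7.3.2 says the change "from baseline and last follow-up visit will be calculated". For FPG, 7.3.3 says "the change of FPG from baseline and last follow-up visit will be calculated". The last follow-up visit is not defined.

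**SAP.** Sections 5.1, 6.2 and 7.3 place all four endpoints at last visit. The SAP 5.1 footnote reads: "Last visit: The last visit point that measured HbA1c after administration of Trajenta".

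**Data collection.** Protocol 5.2.2 states, for FPG, that "FPG should be collected within 1 month prior to baseline and after 12 weeks and 24 weeks of treatment", and says the same for HbA1c. Section 6.1 describes a "recommended visit schedule - Visit 2 : 12±2 weeks/ Visit 3 : 24±2 weeks", and 7.4 says that no investigations are required.

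**Analysis set and subsets.** SAP 3.2 excludes patients outside the safety set (which itself drops those with incomplete safety follow-up, SAP 3.1) and patients lacking HbA1c. It does not ask for a week-24 value. SAP 6.2 and 7.3 also plan results by length of administration, cut at 24 weeks, and by prior DPP-4 inhibitor use, still at last visit.

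**The concern.** An endpoint named at 24 weeks should have a result at 24 weeks. Under the SAP rule the overall HbA1c change, responder rates and FPG change pool week-24 values with whatever earlier value was the last one available. A reader of the final report could take the pooled figure for the 24-week endpoint. The planned tables would not show the Visit 3 result, how many patients had one, or how many last values came from outside the 24±2-week window.

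The case is clearest for the responder rates, because no protocol section supports last-visit timing for them. For HbA1c and FPG change the SAP settles an unclear protocol term in favour of the last available value, without saying so.

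**Working it through.** **1. Timing side by side**

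| Endpoint | Protocol 5.2.1 | Protocol 7.3.2 / 7.3.3 | SAP 5.1, 6.2, 7.3 |
|---|---|---|---|
| HbA1c change | 24 weeks | last follow-up visit (undefined) | last visit with HbA1c |
| HbA1c <6.5% | 24 weeks | 24 weeks | last visit with HbA1c |
| Lowering ≥0.5% | 24 weeks | 24 weeks | last visit with HbA1c |
| FPG change | 24 weeks | last follow-up visit (undefined) | last visit |

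Rows 2 and 3 are a plain departure of SAP from protocol. Rows 1 and 4 depend on how the undefined term is read: as Visit 3, or as the last visit attended.

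**2. Can an early value enter?** Yes. The schedule is recommended, tests are not required, and SAP 3.2 sets no time for the post-treatment HbA1c. A patient who completes safety follow-up but has HbA1c only at Visit 2 is analysed with that value.

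**3. Do the duration subsets replace a Visit 3 table?** No. A patient treated for 24 weeks or more can still contribute a week-12 HbA1c. In the other direction, the Visit 3 window of 24±2 weeks runs from day 154 to day 182, which is 29 days, and 14 of them (48%) fall before day 168. If administration is counted to the Visit 3 date, a patient seen on one of those days is on schedule but classed as short-term. The cut is also worded differently: SAP 6.2 puts exactly 24 weeks in the long-term set, while SAP 7.3 asks for more than 24 weeks.

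**4. Possible size.** The documents give no figure to reproduce. Planned enrolment of 3,000 is the only input from them. The rest is assumed:
- share of early last values p = 0.05-0.40
- difference in mean between early last values and Visit 3 values d = 0.05-0.20 HbA1c points, in either direction
- SD of change, and of on-treatment HbA1c, 0.8-1.2
- n = 2,000-3,000

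*Mean change.* Last-visit mean minus Visit 3 mean = p × d.
- Smallest: 0.05 × 0.05 = 0.0025. Largest: 0.40 × 0.20 = 0.08.
- 95% CI half-width = 1.96 × SD/√n: 1.96 × 0.8/√3,000 = 0.029, up to 1.96 × 1.2/√2,000 = 0.053.
- Share at which the shift equals the half-width (half-width/d): 14-26% for d = 0.2; 29-53% for d = 0.1; 57% or more for d = 0.05, which is outside the assumed range.

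*Responder rates.* Shift = p × |Φ((c − m ∓ d)/SD) − Φ((c − m)/SD)|, with normal values, cut-off c and Visit 3 mean m.
- Lowering of at least 0.5% (c = −0.5, m = −0.5 to −0.9, rate 50-69%): shift 0.1 to 4.0 percentage points. The maximum is at m = −0.6, SD 0.8, early mean −0.4: 0.40 × (55.0 − 45.0) = 4.0. Half-width 1.7-2.2.
- Below 6.5% (c = 6.5, m = 6.8 to 7.4, rate 13-40%): shift 0.1 to 3.9 points. The maximum is at m = 6.8, SD 0.8, early mean 6.6: 0.40 × (45.0 − 35.4) = 3.9 before rounding of the rates. Half-width 1.2-2.1.

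The half-width is only a yardstick here, because nothing is tested for confirmation.

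**The case against.** **The protocol may not contradict itself.** The flow chart has only two follow-up visits, and protocol 6.2.2 follows every enrolled patient for 24 weeks, so last follow-up visit can naturally mean Visit 3. This stands. A reader might infer a firm conflict between 5.2.1 and 7.3.2/7.3.3; the text supports only an undefined term. It does not help the SAP: if the term means Visit 3, the SAP departs on all four endpoints, not two.

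**The overall results may be close to the 24-week results.** This also stands. They differ only to the extent that patients lack a week-24 HbA1c, and dropping patients with incomplete safety follow-up should reduce that number. The documents do not support saying that the last-visit results are biased, or in which direction. Any difference also mixes time on treatment with differences between patients.

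**The long-term subset is already close.** It is the nearest planned output and covers all four endpoints, but step 3 shows why it is not the Visit 3 result.

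**FPG.** One could infer that a week-24 FPG taken without an HbA1c is discarded. The definition of last visit does rest on HbA1c, but in the available text the footnote is attached to the HbA1c bullet and not to the FPG bullet. So this is a point to clarify, not a shown loss of data.

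**Stakes.** Effectiveness is the secondary objective and no hypotheses are tested. Nothing here affects error control.

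**Conclusion.** The point holds as a mismatch in timing and a missing table. For both HbA1c responder rates the SAP departs from protocol 5.2.1 and 7.3.3. For HbA1c and FPG change it adopts a last-available value where the protocol is ambiguous. No table in SAP 7.3 reports any of the four endpoints at Visit 3.

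The practical size is unknown. It is negligible if few patients lack a week-24 value. In the upper part of the assumed range the shift exceeds the confidence half-width, both for the mean and for the responder rates. Those ranges rest wholly on assumed shares, differences and SDs; in particular, the 40% upper share has no source in the documents. The change should be made because it is cheap and lets the report answer the endpoints it names, not because a distortion has been shown.

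**What to change.** Change the SAP only; no protocol amendment is needed.

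- In 5.1, 6.2 and 7.3, add all four endpoints at Visit 3 (24±2 weeks), with the number of patients having a value, as the result for the stated 24-week endpoints.
- Keep the last-visit results beside them, labelled as such, with the numbers of last values from before and from after the window. Late values need counting too, because the schedule is only recommended.
- State that FPG at Visit 3 is taken from its own measurement, whether or not HbA1c was measured.
- State how the protocol's last follow-up visit is read.
- Use one wording for the 24-week cut in 6.2 and 7.3.

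**Cost.** One extra set of tables, from data the visit schedule already collects. The Visit 3 result has fewer patients. With 5-40% lacking a value and SD 1.0, the half-width for mean change rises from 0.036 (n = 3,000) to 0.037 (n = 2,850) up to 0.046 (n = 1,800). Starting from n = 2,000 it rises from 0.044 to 0.045-0.057. With no imputation, the Visit 3 result covers only patients who stayed and were tested, so it may be selective, for example towards better responders. The SAP should say so; this is why both results are shown with their numbers.
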